6.3 Visit 2 or 3 (Day 30 +/-5): RA cohort only

- Review of medications will be performed;
- Vitals will be recorded and the patient will have a physical exam;
- DAS28, CDAI, RAPID3 and MDHAQ will be performed and recorded;
- ACR responses will be measured;
- Fasting blood will be collected;
- For each subject, no more than 75 cc of blood will be collected in red (no anticoagulant) top, Pax gene tube for genomics, lavender (EDTA anticoagulant) top, green (heparin) and blue (sodium citrate anticoagulant) top tubes. Approximately 40 cc of blood will be used for the different measurements of platelet function, inflammation, immune activation, and other markers of cardiovascular risk, and approximately 30 cc of blood will be used to purify cells, RNA and DNA and then stored in -80C/liquid nitrogen for genetic and functional profiling. The results of the genetic testing will not be shared with the subjects.
- Fasting brachial artery reactivity testing including one time dose of 0.4 mg of nitroglycerin given sublingual. To minimize risk of hypotension, nitroglycerin will not be administered if resting systolic blood pressure is <100 mmHg;
- Adverse events will be reviewed and recorded;
- Medication compliance will be reviewed with the subject.

7 Sample storage for future research

The samples will be stored in the PI's lab without any identifying information other than a code number. The code number will not be based on any information that could be used to identify the subject (for example, social security number, initials, birth date, etc). The master list linking names to code numbers will be kept in a locked file cabinet, separate from all research information. All specimen handling, collection, processing, and storage, will be performed as per regulations and Tisch Laboratory and NYU policy. Specimens will be

CONFIDENTIAL

collected at CMC and transferred to Tisch Laboratory for analysis. Samples will be stored for 10 years after the end of the study, if subjects give permission in their consent form.

7.1 **Optional permission to store samples for future use**

Subjects have the option to allow researchers to store their blood samples for future research, either for new research studies or in order to run additional tests on blood collected as part of this study. The consent form has a section that will allow subjects to explicitly grant permission for this by checking a box and initialing. This permission to store samples for future use is completely optional and voluntary. Samples kept for future research after the duration of this study will be stored in the same manner as they were stored during the course of the study. The samples will be stored in the lab of the PI, [name], located at New York University Langone Health, [name]. Samples would be stored for 10 years after the end of the study and then destroyed. Subjects may request, in writing, for their samples to be destroyed if they change their mind or for any other reason. The purpose of this possible future research is unknown, but will have the purpose of contributing to medical knowledge and understanding of human health. Genetic testing will not be performed on stored samples. The stored samples will be available to the PI of this study and all co-investigators. Any new information derived from stored samples will be kept in a secure database matching all of the confidentiality requirements of any database use in this study. Samples will not be shared with other researchers outside the scope of this study.

8 **Statistical Plan**

The primary end point of the trial is the Disease Activity Score for 28-joint counts (DAS28) at 30 days after randomization. The DAS28 is a composite index of the number of swollen and tender joints, the erythrocyte sedimentation rate, and a visual-analogue scale of patient-reported disease activity.(Prevoo et al., 1995) A decrease in the DAS28 of 1.2 or more is considered to be a clinically meaningful improvement.(van Gestel et al., 1996; Ward et al., 2014) A total of 25 subjects with RA would have 90% power to detect a before- and after difference of 1.2 in the DAS28 at 30 days (assuming a SD of 1.5), with a two-sided type I error of 5%, and a 20% attrition rate.

Power and sample size analysis was performed to investigate appropriate sample size for evaluating platelet activity markers in subjects with RA versus age- and sex matched OA controls. Since patients with RA have a heightened inflammatory phenotype and at higher cardiovascular risk than osteoarthritis, we hypothesize that the mean measurement of platelet markers for RA is 35% greater (similar to previously demonstrated differences in high risk phenotypes) than age- and sex matched OA controls for each measurement. Based on two-sided two-sample t-tests with 25 patients in the RA group and 10 patients in the OA group, our power is listed in the table for each measure of platelet measure at the 0.05 significance level using mean/SDs from preliminary data in healthy controls.

Measurement	Power
Platelet Aggregation*	91%
PAC-1	87%
Monocyte platelet aggregates	94%
Leukocyte platelet aggregates	93%

**Powered for low-dose epinephrine based on preliminary data (as described above)*

CONFIDENTIAL

If patients with RA do not have an increased platelet (and inflammatory) phenotype compared with OA – that would be an important finding we will report in this study.

9 Safety and Adverse Events

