1.2 Investigational Agent

This study is looking at the investigational agent ticagrelor. Subjects who are already receiving MTX at stable doses of 10 to 25 mg weekly for at least 12 weeks will receive 90 mg of ticagrelor given orally bid. Ticagrelor is an oral, direct-acting, reversibly binding P2Y₁₂ receptor antagonist, that is approved for the treatment of patients with acute coronary syndrome and prior myocardial infarction. In addition to its antiplatelet effects, ticagrelor can inhibit adenosine cell uptake, likely through inhibition of the equilibrative nucleoside transporter 1. Ticagrelor also significantly increases coronary blood flow velocity via an adenosine mediated mechanism.

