1.4 Dose Rationale

Ticagrelor 90 mg twice daily will be used in this study. This dose was chosen based on ticagrelor's antiplatelet effect at this dose and use in other indications (acute coronary syndrome, prior myocardial infarction). In addition, there is a concentration-dependent response for ticagrelor in vitro in terms of conservation of added adenosine to whole blood. There is also an effect on adenosine induced coronary blood flow of a 180mg loading dose of ticagrelor in healthy subjects (Wittfeldt 2013) and after 90mg in ACS patients (Alexopolous 2013). This effect is mediated by inhibition of the adenosine transporter ENT1 (type 1 equilibrative nucleoside transporter), which provides protection for adenosine from intracellular metabolism, thus increasing its concentration and biological activity. Study medication will be taken orally, twice a day. Safety and tolerability will be monitored closely during the study. The 30-day study duration is considered sufficient to investigate acute safety and efficacy in ticagrelor in RA.

CONFIDENTIAL

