3.1 General Design

This is an open label study to assess the improvement in the Disease Activity Score for 28-joint counts (DAS28) with ticagrelor given at 90 mg twice daily in patients with RA who have active disease despite MTX therapy (as defined by the inclusion/exclusion criteria). There will also be a cross sectional analysis of baseline platelet activity in subjects with rheumatoid arthritis and osteoarthritis. Subjects in the OA cohort will not receive any study medication, and will only have one study visit.

Patients will receive 90 mg ticagrelor orally twice daily. The patients will receive drug for 30-days. Methotrexate will be by prescription as per standard of care and the dose will remain stable throughout the study duration.

A summary of the study design is noted in the Supplemental Figure of Study Design. Briefly, there are 2 major goals: 1) we would like to demonstrate the heightened cardiovascular risk in RA by comparing platelet activity, inflammation and endothelial function in baseline rheumatoid arthritis versus age- and sex-matched patients with osteoarthritis; and 2) we would like to demonstrate the effect of ticagrelor in rheumatoid arthritis by the pre- and post- measures of clinical RA severity, platelet activity, inflammation and endothelial function in rheumatoid arthritis before and after ticagrelor therapy.

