5.1 Administration of Study Drug

Patients will self-administer study medication twice daily, orally for 30 days.

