5.4.2 Return or Destruction of Study Drug

At the completion of the study, there will be a final reconciliation of drug shipped, drug consumed, and drug remaining. This reconciliation will be logged on the drug reconciliation form, signed and dated. Any discrepancies noted will be investigated, resolved, and documented prior to return or destruction of unused study drug. Drug destroyed on site will be documented in the study files.

6 Study Procedures

Study participation includes a 30-day treatment period. Screening and baseline visits may be done on the same day if the subject is able to give fasting blood and does not meet any exclusion criteria.

Table 1: Schedule of Assessments.

	Screening	Baseline	1 and 2 Week Phone call	Day 30
Visit #	1	1 or 2		2 or 3
Day#	- 30 - 3	0		30 ± 5
Informed consent	X			
Medical history	X	X		
Medications	X	X		X
Vital signs/physical exam		X		X
DAS28/CDAI/RAPID3/MDHAQ	X	X		X
ACR responses		X		X
Blood (fasting) collection		X		X
Urine and/or serum pregnancy test for WOCBP only	X	X		
Platelet Activity		X		X
Brachial Artery Reactivity Testing (fasting)		X		X
Dispense study drug		X		
Adverse events	X	X	X	X
Medication compliance/diary			X	X

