6.2 Baseline (Visit 1 or 2, Day 0)

- Medical history and review of medications will be performed;
- Vitals will be recorded and the patient will have a physical exam;
- DAS28, CDAI, RAPID3 and MDHAQ will be performed and recorded;
- ACR responses will be measured by the physician using patient questionnaires and joint counts;
- Fasting blood will be collected;
- For each subject, no more than 75 cc of blood will be collected in red (no anticoagulant) top, Pax gene tube for genomics, lavender (EDTA anticoagulant) top, green (heparin) and blue (sodium citrate anticoagulant) top tubes. Approximately 40 cc of blood will be used for the different measurements of platelet function, inflammation, immune activation, and other markers of cardiovascular risk, and approximately 30 cc of blood will be used to purify cells, RNA and DNA and then stored in -80C/liquid nitrogen for genetic and functional profiling. The results of the genetic testing will not be shared with the subjects.
 - The drawing of a maximum of 75 cc of blood is justified by the need for the above referenced tests, measurements and purification. These tubes will be drawn at the time of the standard of care blood draws for routine patient care monitoring. This amount of blood is medically safe to draw. The physician will always ensure the safety of drawing this volume of blood.
- Fasting brachial artery reactivity testing including one time dose of 0.4 mg of nitroglycerin given sublingual. To minimize risk of hypotension, nitroglycerin will not be administered if resting systolic blood pressure is <100 mmHg;
- Study medication will be dispensed;
- Adverse events will be collected.

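### Dosing is fixed at 30 days but the only outcome visit may fall as late as Day 35, so late-visit patients can have their platelet markers sampled off drug

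*Combined protocol and SAP*

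**What the plan says.** Treatment duration is given three times. Section 3.1: "The patients will receive drug for 30-days". Section 5.1: "Patients will self-administer study medication twice daily, orally for 30 days". The opening of Section 6: "Study participation includes a 30-day treatment period".

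Drug is supplied once. Section 6.2 has "Study medication will be dispensed" on Day 0, and in Table 1 the row "Dispense study drug" is marked only under Baseline. The number of tablets is not stated.

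Outcomes after baseline are measured at a single visit, headed "6.3 Visit 2 or 3 (Day 30 +/-5): RA cohort only", and Table 1 gives the same window. DAS28, fasting blood, platelet activity and brachial artery testing are all done there. The week 1 and week 2 contacts are phone calls.

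The platelet markers in Section 3.3 are ADP-induced aggregation, the VASP index and monocyte-platelet aggregation, each compared with baseline. Section 1.2 describes ticagrelor as "oral, direct-acting, reversibly binding". On the adenosine side, Section 1.4 says "there is a concentration-dependent response for ticagrelor in vitro".

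Section 5.2 calls Day 30 a post-dose visit. No section says whether patients keep taking drug until they are seen, or how soon after a dose blood must be drawn.

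**The concern.** A window of 5 days either side is ordinary. The difficulty is its late half, combined with a fixed stopping point. The off-drug sample would not come from poor adherence, because the written schedule produces it in a fully adherent patient.

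The platelet endpoints are meant to show what taking ticagrelor does. With a reversibly binding drug, time since the last dose bears directly on them, and any loss of inhibition would pull the before-after change toward zero. The study has no control arm, and no drug level is listed among the endpoints. Without a recorded last-dose time, a diluted result could not be told apart from a weak effect.

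**Working it through.** The plan gives no figure for the interval between last dose and sampling, so there is none to reproduce. The sample-size statement in Section 8 does not enter this point.

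**Inputs from the documents.** 30 days, twice daily (Section 5.1); visit on Days 25 to 35 (Section 6.3, Table 1); fasting blood at the visit (Section 6.3); 25 RA completers (Section 4.3).

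**Assumptions.** Doses are 12 hours apart, so 30 × 2 = 60 doses. The visit is in the morning, because sampling is fasting. The morning of Day d is written d.0 and the evening d.5. The first dose falls on Day 0 morning, Day 0 evening or Day 1 morning.

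**Time of last dose** = first dose + 59 × 0.5 days:
- 0.0 + 29.5 = 29.5
- 0.5 + 29.5 = 30.0
- 1.0 + 29.5 = 30.5

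**Gap at the visit** = visit time − time of last dose, in days (negative means dosing is still under way):

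| Visit | First dose 0.0 | First dose 0.5 | First dose 1.0 |
|---|---|---|---|
| Day 25 | −4.5 | −5.0 | −5.5 |
| Day 30 | 0.5 | 0.0 | −0.5 |
| Day 31 | 1.5 | 1.0 | 0.5 |
| Day 32 | 2.5 | 2.0 | 1.5 |
| Day 35 | 5.5 | 5.0 | 4.5 |

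Up to Day 30 no patient is more than one 12-hour interval from a dose. On Day 31 two of the three cases exceed it. From Day 32 all three do. An afternoon visit adds 0.5 day.

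**Tablets to dose through the morning of Day 35** = (35 − first dose)/0.5 + 1 = 71, 70 or 69. That is 11, 10 or 9 beyond 60, or about 5 days' supply.

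**Weight of one late patient.** With 25 completers, each contributes 1/25 = 4% of the mean change. How much of the effect a late patient has lost, and how many patients are late, are not in the documents. The calculation stops there.

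**Adverse event period (separate point).** Section 9.1 runs it to 30 days after the last dose, so it ends at Day 59.5, 60.0 or 60.5. Table 1 has no contact after the outcome visit. Days of that period left without scheduled contact:
- After a Day 35 visit: 59.5 − 35 = 24.5, 60.0 − 35 = 25.0, or 60.5 − 35 = 25.5.
- After a Day 25 visit: all 30, plus the last 4.5 to 5.5 days of dosing as the plan now stands.

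**The case against.** The strongest reply is that the plan means treatment end and outcome visit to be the same event. Section 2 gives 30 days of drug with the outcome at 30 days, Section 3.3 measures endothelial function before and after 30 days of therapy, and Section 5.2 ties the visit to dosing. On that reading the window moves both together. Section 5.4.2 also expects some drug to remain at reconciliation, and 60 tablets is a derived count. This may well be what the authors intended, but the rule is not written. The post-dose label and the reconciliation step do not supply it, and three statements of a fixed 30 days point the other way.

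The second reply is that Table 1 already has a compliance and diary row. That row could hold the last-dose time. The forms are not in the documents, so their content cannot be judged, and nothing in the text requires that item.

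The third reply stands in full: the longest gap applies only to the end of the window, no visit distribution is given, and the markers affected are secondary.

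A reader might go further and infer that the platelet effect has gone by Day 35, or that the primary DAS28 result is compromised. The documents support neither. They give no half-life, offset time or platelet recovery curve. For DAS28 and brachial reactivity there is only the in vitro statement in Section 1.4, so an effect can be neither asserted nor ruled out. Nor does the point reach the RA versus OA comparison, which uses baseline samples.

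On safety, a reader might infer that events after the visit go unrecorded. That is too strong. Section 9.1 has unresolved events followed and tells subjects to report later events believed related, Section 9.2 covers ongoing and late serious events, and Section 4.5.2 follows patients withdrawn for an adverse event. What remains is mainly new events that nobody thinks related, and events on the last dosing days after an early visit.

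**Conclusion.** The point holds as a cheap improvement to the plan. As written, adherent patients seen after about Day 31 are sampled off drug, by 4.5 to 5.5 days at most for a morning visit. This can dilute the three secondary platelet markers. The direction follows from reversible binding, but the size is unknown. The timing figures rest on 60 doses at 12-hour intervals and a first dose between Day 0 morning and Day 1 morning.

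The missing contact after the outcome visit is a separate and minor matter with its own cause. It adds no weight to the timing point.

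**What to change.** In Sections 5.1 and 6.3, state that patients take ticagrelor until the outcome visit, including the last scheduled dose before sampling, and stop at that visit. Amend the fixed 30-day wording in Sections 3.1 and 6 to match. Dispense about 5 days of spare tablets at baseline and collect the remainder at the visit. Record the date and time of the last dose in the existing compliance/diary record.

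The cost is up to about 5 extra days of exposure, with its bleeding risk, for late-visit patients. Exposure would run from about 25 to 35 days instead of a fixed 30. Early-visit patients would stop at about 25 days. The current window already allows their outcomes to be read then, so they lose only doses that fall after their last measurement.

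Separately, add to Table 1 one phone call per RA patient about 30 days after the last dose, asking about adverse events and bleeding. That is about 25 calls, and it gives the recording rule in Section 9.2 a scheduled contact to rest on.

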9.1 Definitions

Unanticipated Problems Involving Risk to Subjects or Others

Any incident, experience, or outcome that meets all of the following criteria:

- Unexpected in nature, severity, or frequency (i.e. not described in study-related documents such as the IRB-approved protocol or consent form, package insert, etc)
- Related or possibly related to participation in the research (i.e. possibly related means there is a reasonable possibility that the incident experience, or outcome may have been caused by the procedures involved in the research)
- Suggests that the research places subjects or others at greater risk of harm (including physical, psychological, economic, or social harm).

Adverse Event

An **adverse event** (AE) is any symptom, sign, illness or experience that develops or worsens in severity during the course of the study. Intercurrent illnesses or injuries should be regarded as adverse events.

Abnormal results of diagnostic procedures are considered to be adverse events if the abnormality:

- results in study withdrawal
- is associated with a serious adverse event
- is associated with clinical signs or symptoms
- leads to additional treatment or to further diagnostic tests
- is considered by the investigator to be of clinical significance

Serious Adverse Event

Adverse events are classified as serious or non-serious. A **serious adverse event** is any AE that is:

- fatal
- immediately life-threatening
- requires or prolongs hospital stay
- results in persistent or significant disability or incapacity
- a congenital anomaly or birth defect
- an important medical event

Important medical events are those that may not be immediately life threatening, but are clearly of major clinical significance. They may jeopardize the subject, and may require intervention to prevent one of the other serious outcomes noted above. For example, drug overdose or abuse, a seizure that did not result in in-patient hospitalization, or intensive treatment of bronchospasm in an emergency department would typically be considered serious.

All adverse events that do not meet any of the criteria for serious should be regarded as **non-serious adverse events**.

Adverse Event Reporting Period

The study period during which adverse events must be reported is normally defined as the period from the initiation of any study procedures to the end of the study treatment follow-up. For this study, the study treatment follow-up is defined as 30 days following the last administration of study treatment.

Preexisting Condition

A preexisting condition is one that is present at the start of the study. A preexisting condition should be recorded as an adverse event if the frequency, intensity, or the character of the condition worsens during the study period.

CONFIDENTIAL

General Physical Examination Findings

At screening, any clinically significant abnormality should be recorded as a preexisting condition. At the end of the study, any new clinically significant findings/abnormalities that meet the definition of an adverse event must also be recorded and documented as an adverse event.

Post-study Adverse Event

All unresolved adverse events should be followed by the investigator until the events are resolved, the subject is lost to follow-up, or the adverse event is otherwise explained. At the last scheduled visit, the investigator should instruct each subject to report any subsequent event(s) that the subject, or the subject's personal physician, believes might reasonably be related to participation in this study. The investigator should notify the study sponsor of any death or adverse event occurring at any time after a subject has discontinued or terminated study participation that may reasonably be related to this study. The sponsor should also be notified if the investigator should become aware of the development of cancer or of a congenital anomaly in a subsequently conceived offspring of a subject that has participated in this study.

Abnormal Laboratory Values

A clinical laboratory abnormality should be documented as an adverse event if any one of the following conditions is met:

- The laboratory abnormality is not otherwise refuted by a repeat test to confirm the abnormality
- The abnormality suggests a disease and/or organ toxicity
- The abnormality is of a degree that requires active management; e.g. change of dose, discontinuation of the drug, more frequent follow-up assessments, further diagnostic investigation, etc.

Hospitalization, Prolonged Hospitalization or Surgery

Any adverse event that results in hospitalization or prolonged hospitalization should be documented and reported as a serious adverse event unless specifically instructed otherwise in this protocol. Any condition responsible for surgery should be documented as an adverse event if the condition meets the criteria for an adverse event.

Neither the condition, hospitalization, prolonged hospitalization, nor surgery are reported as an adverse event in the following circumstances:

- Hospitalization or prolonged hospitalization for diagnostic or elective surgical procedures for a preexisting condition. Surgery should **not** be reported as an outcome of an adverse event if the purpose of the surgery was elective or diagnostic and the outcome was uneventful.
- Hospitalization or prolonged hospitalization required to allow efficacy measurement for the study.
- Hospitalization or prolonged hospitalization for therapy of the target disease of the study, unless it is a worsening or increase in frequency of hospital admissions as judged by the clinical investigator.

